#### 9.2.3 Safety Analysis Plan

Safety and tolerability data will first be analyzed for each cohort after the first dose(s) and evaluated by an external DMC.

All safety and tolerability parameters (adverse events, vital signs, laboratory monitoring, and physical examination results) will be listed by patient and cohort.

Analyses based on data from repeat dosing from Cohort 1, 2, and 3 with OCTA101 for 3 months will be analyzed separately from data related to the first doses. In these analyses, data will be presented by cohort and overall. Data from single doses after the completion of the repeat dosing will be analyzed separately. All data will be presented together without reference to the original cohort.

Data from Cohort 6 will be analyzed separately and will be split by period (run-in period with Nuwiq and OCTA101 treatment period) and by planned OCTA101 daily dose.

All AEs reported during the study will analyzed and presented. AEs starting at or after the first dose of IMP will be presented separately from those starting prior to the first dose of IMP. For Cohort 6, AEs starting at or after the first dose of Nuwiq and prior to the first dose on OCTA101 will be presented separately from AEs starting after the first dose of OCTA101.

The number and percentage of patients with AEs and the number of AEs will be summarized by primary MedDRA System Organ Class and Preferred Term. Separate tables showing all AEs, all serious AEs and all AEs at least possibly related to IMP will be generated. Further a summary of AEs by severity, presenting the most severe event per patient overall and within each SOC and PT will be generated.

For thromboembolic events and local injection site reactions, appropriate clusters of MedDRA terms will be defined and such events will be presented within these clusters, using the summaries detailed above.

The frequencies of local injection reactivity ratings by the investigator and the patient (see Section 7.4.1) directly after injection and  $15 \pm 5$  min post-injection will be summarized over the whole daily treatment period using the number of injections as denominator. Further, the worst rating per patient and time period will be summarized. Visual analogue scale assessments of injection site pain will be summarized analogously.

The frequencies (including percentages) of any inhibitor formation to FVIII and antibody formation to OCTA12 will be presented by cohort and overall. Inhibitor formation to FVIII will be considered if at least one result of neutralizing antibody was equal or greater than 0.6 BU/mL. Antibody formation to OCTA12 will be defined as positive if at least one result of OCTA12 antibody was positive at any visit during the study. Results from LumiTope assay will be listed.

Vital sign and safety laboratory parameters will be analyzed using descriptive statistics for measured values and for changes from pre-dose values to each single injection.

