#### Statistical Analysis Plan:

Safety and tolerability data will first be analyzed for each cohort after the first dose(s) and evaluated by an external DMC. Two separate analyses will be performed: the first one will include all available data of enrolled patients in Cohorts 1, 2, 3, and 5 and the second one will include all data of the newly defined Cohort 6. Analyses based on data from repeat dosing

Protocol Identification Code: SubQ8-01	ission
Date of Final Protocol: 30-Jul-2021	
	Protocol Identification Code: SubQ8-01 Date of Final Protocol: 30-Jul-2021

from Cohort 1, 2, and 3 with OCTA101 for 3 months will be analyzed separately from data related to the first doses. In these analyses, data will be presented by cohort and overall. Analysis based on Cohort 6 data will be presented by period (run-in period with Nuwiq and OCTA101 treatment period) and by planned OCTA101 daily dose.

For each cohort

- Descriptive analysis of demographic and baseline variables.
- Safety analyses

The number and percentage of patients with AEs and the number of AEs will be summarized by primary MedDRA System Organ Class (SOC) and Preferred Term (PT). Separate tables showing all AEs, all serious AEs and all AEs at least possibly related to IMP will be generated. Further a summary of AEs by severity, presenting the most severe event per patient overall and within each SOC and PT will be generated.

For thromboembolic events and local injection site reactions, appropriate clusters of MedDRA terms will be defined and such events will be presented within these clusters, using the summaries detailed above.

The frequencies of local injection reactivity ratings by the investigator and the patient will be summarized over time periods. The frequencies (including percentages) of any inhibitor formation to FVIII and antibody formation to OCTA12 will be presented. Vital sign and safety laboratory parameters will be analyzed using descriptive statistics for measured values and for changes from pre-dose values to each single injection.

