- Cohort 1 and 2 (n=8): single-period investigation with a single sc dose of 50 IU/kg OCTA101 profiled up to 120 hours after dosing for FVIII and up to 21 days for OCTA12.
- Cohort 3: 50 IU/kg (n=8): two-period investigation of a single iv dose of 50 IU/kg Nuwig profiled for up to 72 hours after dosing followed by sc dose of 50 IU/kg OCTA101 administered into the abdomen profiled up to 72 hours. Treatments were to be administered in fixed sequence, with Nuwig first.
- Cohort 4: 50 IU/kg (n=4): Cancelled.
- Cohort 5 (n=4): three-period investigation of single sc doses of 20, 40, and 60 IU/kg OCTA101 profiled up to 72 hours after dosing, respectively. Treatments were to be administered in fixed dose-ascending sequence.
- Cohort 6 (n  $\geq$ 16): Following an initial 4 to 6-week run-in period with Nuwiq iv prophylaxis, >3-6 months daily prophylactic treatment with 12.5 IU/kg OCTA101 sc, then 25 IU/kg OCTA101 sc for a further 6-7 months (exact dosing depends on available vial sizes). In case of two spontaneous bleeding episodes, after having completed at least 3 months with 12.5 IU/kg OCTA101 daily treatment the individual treatment dose was planned to be increased from 12.5 to 25 IU/kg. Site of administration (abdomen or thigh) to be chosen by the patient. A further treatment phase with 40 IU/kg OCTA101 was planned to be discussed with the DMC, once results of earlier dosing phases are available.

The DMC will review and assess the available results approximately every 3 months.

Property By DMC-recommendation, patients enrolled in Cohorts 1, and 2 proceeded to the 3-month prophylactic treatment part of the study and received daily dosing (approximately 40-60 IU/kg;

dose chosen to allow administration by single injection; it was permitted to daily alternate the vial, e.g. 3000 IU on one day 1, 5000 IU on day 2, 3000 IU on day 3, 5000 IU on day 4 etc.) of OCTA101 for 3 months (home treatment). Patients from Cohort 1 received prophylactic Nuwiq (home treatment) until the DMC had confirmed that OCTA101 could be used as daily prophylaxis. Bleeding events during the study were treated with Nuwig. Throughout this part of the study, FVIII inhibitors, plasma concentrations of FVIII:C, and OCTA12 were measured repeatedly.

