#### **Dose and Dosing Schedule** 5.4

The following will be administered at the study site by trained personnel:

Cohort 1: Single injection of OCTA101 50 IU/kg sc with 72 hours of observation.

- Cohort 2: Single injection of OCTA101 100 IU/kg sc with 96 hours of observation.
- Cohort 1 and 2: PK assessment after 3-month daily dosing: Single injection of OCTA101 50 IU/kg sc with 120 hours of observation for FVIII and 21 days of observation for OCTA12.
- Cohort 3: Single injection of Nuwiq 50 IU/kg iv with 72 hours of observation, followed by single injection of OCTA101 50 IU/kg sc administered into the abdomen with 72 hours of observation.
- Cohort 4: (Cancelled) Single injection of OCTA101 50 IU/kg sc administered into the thigh with 72 hours of observation.
- Cohort 5: Single injection of OCTA101 20 IU/kg sc with 72 hours of observation, followed by single dose of OCTA101 40 IU/kg sc with 72 hours of observation, followed by single dose of OCTA101 60 IU/kg sc with 72 hours of observation.
- Cohort 6: 4-6 weeks prophylactic run-in treatment phase with ~30 IU/kg Nuwiq iv, given 3 x weekly, followed by 2 (probably 3) phases of 6-7 months daily injection with OCTA101, first 12.5 IU/kg, followed by 25 IU/kg daily (and probably 40 IU/kg). No wash-out periods are required between the treatment phases. Patients reporting two spontaneous bleeding episodes during the 12.5 IU/kg treatment phase may immediately switch to the 25 IU/kg daily, if they have completed at least 3 months with 12.5 IU/kg. Nuwiq (according to SmPC) is used to control bleeding episodes, if any.

In all cases, the minimum number of injections required to provide the required dose must be administered. If multiple injections are needed, then they should not be administered at the same spot. The PK doses were to be achieved as accurately as possible with the available vial strengths as a single injection; it was permitted to daily alternate the vial size, (e.g. 3000 IU on one day 1, 5000 IU on day 2, 3000 IU on day 3, 5000 IU on day 4 etc.).

OCTA101 will be administered by sc injection into the abdomen or thigh (see Appendix 1 in Section 13.a), whereby for Cohorts 1 and 2 the choice is up to the investigator and patient, in Cohort 3 all administrations of OCTA101 will be into the abdomen, in Cohort 5, four patients each will consistently be injected with OCTA101 either in the abdomen or in the thigh at all three dose levels.

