# 7.3.2.2 Collection of AEs

The condition of the patient will be monitored throughout the study. At each visit, whether scheduled or unscheduled, AEs will be elicited using a standard nonleading question such as "How have you been since the last visit/during the previous study period?" In addition, the Investigator will check the patient diaries (if applicable) for any documented event.

Any AE or ADR which occurs during the study will be noted in detail on the appropriate pages of the eCRF. If the patient reports several signs or symptoms representing a single syndrome or diagnosis, the diagnosis should be recorded in the eCRF. The Investigator will grade the severity of all AEs or ADRs (mild, moderate, or severe), the seriousness (non-serious or serious), and the causality as defined in Sections 7.3.2.3, 7.3.3, and 7.3.2.4. The Sponsor is responsible for assessing the expectedness of each ADR (expected or unexpected) as defined in Section 7.3.2.5.

In the event of clinically significant abnormal laboratory findings, the tests will be confirmed, and the patient followed up until the laboratory values have returned to normal and/or an adequate explanation for the abnormality has become available.

Diseases, signs and symptoms, and/or laboratory abnormalities already present before the first administration of IMP will not be considered AEs unless an exacerbation in intensity or frequency (worsening) occurs.

The Investigator will provide detailed information about any abnormalities and about the nature of and reasons for any action taken as well as any other observations or comments that may be useful for the interpretation and understanding of an AE or ADR.

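### Cohort 6 adverse events are summarised as patient percentages and counts over periods of very unequal length, with no person-time, so reading them across dose levels is confounded by time observed

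*Protocol*

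**What the plan says.** AEs head the list of primary endpoints (Protocol 3.1.1), and the primary objective is the safety of various OCTA101 doses (Protocol 2.1).

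For Cohort 6, Protocol 9.2.3 states: "Data from Cohort 6 will be analyzed separately and will be split by period (run-in period with Nuwiq and OCTA101 treatment period". It then adds the planned daily OCTA101 dose as a second split. The Study Outline says the same: "Analysis based on Cohort 6 data will be presented by period (run-in period with Nuwiq and" the OCTA101 period, again by planned dose. AEs that start in the run-in, "prior to the first dose on OCTA101 will be presented separately from AEs starting after the first dose of OCTA101".

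The metric is given once for all AE tables: "The number and percentage of patients with AEs and the number of AEs will be summarized" by MedDRA class and preferred term. The tables for serious AEs, related AEs and AEs by severity, and the clusters for thromboembolic events and injection site reactions, use the same summaries. No patient-time, rate or common observation window is named for AEs.

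The period lengths come from the dosing sections:

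- Run-in: "4-6 weeks prophylactic run-in treatment phase with ~30 IU/kg Nuwiq iv, given 3 x weekly" (Protocol 5.4).
- 12.5 IU/kg: ">3-6 months daily prophylactic treatment with 12.5 IU/kg OCTA101 sc" in the cohort summary of Protocol 3.2. The same section, further up, allows more than 3 and up to 6-7 months, and 5.4 gives 6-7 months.
- 25 IU/kg: 6-7 months (Protocol 3.2 and 5.4).
- A patient with two spontaneous bleeds can move to 25 IU/kg once 3 months at 12.5 IU/kg are complete (Protocol 5.4).

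Protocol 9.4 describes safety comparison as descriptive and extends these analyses to Cohort 6.

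**The concern.** The percentage of patients with at least one AE, and the number of AEs, both grow with the time observed. Columns that cover a few weeks, three months and seven months will differ even if the underlying risk is the same in all of them.

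The contrast that matters most is 12.5 against 25 IU/kg, because the objective concerns safety across doses and because the DMC advises on moving to 25 IU/kg and on whether to open a 40 IU/kg phase. The length of the 12.5 IU/kg phase also depends on the patient's own bleeding, so the two dose columns need not carry the same follow-up even within a patient.

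The protocol accounts for exposure elsewhere. Bleeding is annualised (9.2.2), and local reactivity ratings and pain scores use the number of injections as denominator (9.2.3). AEs have neither.

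**Working it through.** The plan states no AE rate, power or sample size calculation, so there is no figure of its own to reproduce. The check has two parts: the ratio of period lengths, and what equal underlying rates would look like in the planned metric.

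**Inputs**

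- Run-in 4-6 weeks; 12.5 IU/kg more than 3 and up to 7 months; 25 IU/kg 6-7 months (Protocol 3.2 and 5.4).
- 16 evaluable patients (Protocol 3.2).
- 1 month = 365.25/12/7 = 4.348 weeks.
- Assumed AE rate r of 0.5, 1, 2 or 4 per patient-year, constant and identical in every period. This is not from the documents.

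**Step 1: length ratios**

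- Shortest OCTA101 phase against longest run-in: 3 × 4.348 / 6 = 13.0 / 6 = 2.2.
- Longest phase against shortest run-in: 7 × 4.348 / 4 = 30.4 / 4 = 7.6.
- A 6-month phase: 26.1 / 6 = 4.3 to 26.1 / 4 = 6.5.
- 25 against 12.5 IU/kg: from 6 / 7 = 0.86 to 7 / 3 = 2.3.

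**Step 2: percentage of patients with at least one AE**, P = 1 − exp(−r·t), with t in years

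| r per patient-year | 4 weeks | 6 weeks | 3 months | 6 months | 7 months |
|---|---|---|---|---|---|
| 0.5 | 3.8% | 5.6% | 11.8% | 22.1% | 25.3% |
| 1 | 7.4% | 10.9% | 22.1% | 39.3% | 44.2% |
| 2 | 14.2% | 20.5% | 39.3% | 63.2% | 68.9% |
| 4 | 26.4% | 36.9% | 63.2% | 86.5% | 90.3% |

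Example for r = 2: 4 weeks is 28/365.25 = 0.077 years, so P = 1 − exp(−0.153) = 14.2%; 6 months is 0.5 years, so P = 1 − exp(−1) = 63.2%.

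For the dose contrast at r = 2, patients who leave 12.5 IU/kg at 3 months would show 39%, against 63-69% over 6-7 months at 25 IU/kg, with no dose effect at all.

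**Step 3: expected number of AEs in 16 patients**, 16·r·t at r = 2

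- Run-in: 2.5 (4 weeks) to 3.7 (6 weeks).
- OCTA101 phase: 8.0 (3 months), 16.0 (6 months), 18.7 (7 months).

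**Step 4: the same data as a rate**

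- Run-in of 6 weeks: 16 × 0.115 = 1.84 patient-years; 3.7 / 1.84 = 2.0 per patient-year.
- 3 months: 8.0 / (16 × 0.25) = 2.0. 6 months: 16.0 / (16 × 0.5) = 2.0.

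The excess due to duration disappears.

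**Step 5: precision**

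Sixteen patients over a mid-range 5-week run-in give 16 × 35 / 365.25 = 1.5 patient-years. Three events there give an exact Poisson 95% interval of about 0.4 to 5.7 per patient-year, so a run-in rate will be imprecise.

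**The case against.** **No comparison with Nuwiq is planned.** A reader might infer that the tables make OCTA101 look worse than Nuwiq by construction. The documents do not support that. Run-in AEs are shown separately, the Study Outline lists no reference therapy, Protocol 3.3.2 names Nuwiq as a control only for bioavailability in Cohort 3, and Protocol 1.5 gives possible tolerance induction as the reason for the run-in. No decision rule turns on an AE percentage. This stands, and it limits the point to descriptive reading across dose levels, and against the run-in only if someone makes that comparison.

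**AE questioning is not absent from the run-in.** A reader might also count the columns of Flow Chart 9 and infer no elicitation during the run-in against eight visits per OCTA101 phase. That is not supported either. Protocol 7.3.2.2 says "At each visit, whether scheduled or unscheduled, AEs will be elicited", with a question that reaches back to the previous visit or period, so the visit that starts OCTA101 collects run-in AEs. Diaries are checked as well, and in Cohort 6 they start with the first Nuwiq injection (5.7.2). That gives one elicitation per 4-6 weeks in the run-in, against seven later visits in 6 months, or one per 26.1 / 7 = 3.7 weeks. A narrower difference remains: no safety laboratory tests or vital signs are scheduled within the run-in, and the AE definition includes abnormal laboratory findings.

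**The Cohort 6 SAP is a separate document that was not supplied.** It may add rates. This stands: the point can be made only of the protocol. The protocol does not require rates, and the supplied SAP for the earlier cohorts (8.8.3) plans only numbers and percentages for treatment-emergent AEs, although its 8.8.1 summarises drug exposure.

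**The size is hypothetical.** It rests on an assumed rate and a constant hazard. This stands for the percentages, but the length ratios come from the documents.

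**Conclusion.** The point holds as a matter of reporting. In Cohort 6 the stated AE metric mixes dose or period with time observed. The length ratios (2.2 to 7.6 for an OCTA101 phase against the run-in, up to 2.3 for 25 against 12.5 IU/kg) follow from the protocol alone. The percentages, such as 14-21% against 39%, 63% and 69%, illustrate a rate of 2 per patient-year that is assumed constant and equal in all periods; under that kind of assumption the direction is the same at any non-zero rate.

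No test or error rate is affected, because the analysis is descriptive. The risk is that a rise in AE percentage from one dose level to the next is read as a dose effect, or that a real one is put down to longer follow-up, and the planned tables could not settle which. The injection-based summaries of local reactivity and pain lie outside this point.

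**What to change.** In Protocol 9.2.3 and the Cohort 6 SAP:

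1. Add to each AE table, by period and dose level, the patient-years of observation and the AE rate per patient-year, for all, related and serious AEs. Let each patient's time at 12.5 IU/kg end at the actual switch to 25 IU/kg.
2. Give intervals that allow for repeat events within a patient, or base exact Poisson intervals on each patient's first event. Exact Poisson intervals on all events would treat repeat AEs in one patient as independent.
3. Add a supportive table of AEs in an early window of each OCTA101 phase, with the window set to each patient's own run-in length.
4. Footnote these tables to say that no safety laboratory tests or vital signs are scheduled within the run-in, and that route and injection frequency differ (iv three times weekly against sc daily).
5. Reconcile the stated lengths of the 12.5 IU/kg phase, since they define the follow-up.

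The cost is a few extra table columns and one extra table. Dosing dates are already recorded in the diary (Protocol 5.7.2), so no new data are needed. The drawbacks are that a rate assumes a roughly constant hazard, which the early-window table partly offsets, and that run-in rates will be imprecise at about 1.5 patient-years. Rates remove the effect of duration but not the differences in monitoring or route.

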#### 9.2.4 Handling of Missing Data

In general, missing data will not be imputed. Any specific rule or convention needed for the statistical analysis to account for possibly missing data will be detailed in the SAP.

#### 9.3 Randomization, Stratification, and Code Release

Not applicable for this open-label study based on sequential cohorts.

#### 9.4 Interim Analysis

After the completion of each cohort, PK and safety data were analyzed and discussed during a DMC meeting. Data from each cohort were analyzed separately. Safety data were compared descriptively and no adjustment of a significance level will be performed. These analyses will also be performed for Cohort 6 for safety and efficacy data.

One separate interim analysis will be performed: this will include all available data of enrolled patients in Cohorts 1, 2, 3, and 5.

## 10 ETHICAL/REGULATORY, LEGAL AND ADMINISTRATIVE ASPECTS

#### **10.1 Ethical/Regulatory Framework**

This study will be conducted in accordance with the ethical principles laid down in the Declaration of Helsinki. The study protocol and any subsequent amendment(s) will be submitted to an Independent Ethics Committee (IEC)/Institutional Review Board (IRB) and to

the Regulatory Authority. The study will be conducted in compliance with the protocol, GCP guidelines, and applicable regulatory requirements.

ission The regulatory application or submission for regulatory approval will be made by the Sponsor or designated third party (e.g., CRO) as required by national law.

#### **10.2 Approval of Study Documents**

The study protocol, a sample of the patient information and informed consent form, any other materials provided to the patients, and further requested information will be submitted by the Sponsor or the Investigator to the appropriate IEC/IRB and the Regulatory Authority. The study must be approved by the IEC/IRB and the Regulatory Authority before any IMP may be shipped to the study sites and any patient is exposed to a study-related procedure.

The Sponsor, the Investigator, and any third party (e.g., CRO) involved in obtaining approval must inform each other in writing that all ethical and legal requirements have been met before the first patient is enrolled in the study.

#### **10.3 Patient Information and Informed Consent**

The Investigator will obtain freely given written consent from each patient after an appropriate explanation of the aims, methods, anticipated benefits, potential hazards, and any other aspect of the study which is relevant to the patient's decision to participate. The informed consent form must be signed, with name and date and time noted by the patient, before the patient is exposed to any study-related procedure, including screening tests for eligibility.

The Investigator will explain that the patients are completely free to refuse to enter the study or to withdraw from it at any time, without any consequences for their further care and without the need to justify. The Investigator will complete the informed consent section of the eCRF for each patient enrolled.

Each patient will be informed that his medical (source) records may be reviewed by the study monitor, a quality assurance auditor, or a health authority inspector, in accordance with applicable regulations, and that these persons are bound by confidentiality obligations.

